#### **4.5.3      Physical Examinations**

A complete physical examination, performed at screening and other specified visits, should include an evaluation of the head, eyes, ears, nose, and throat, and the cardiovascular, dermatologic, musculoskeletal, respiratory, gastrointestinal, genitourinary, and neurologic systems.

Limited, symptom-directed physical examinations, including an abdominal examination, should be performed at specified visits and as clinically indicated. Changes from abnormalities identified at screening should be recorded in patient notes.

Any abnormality identified at screening or prior to initiation of study treatment should be recorded on the General Medical History and Baseline Conditions eCRF (unless considered related to a protocol-mandated intervention; see Section 5.3.1). After initiation of study treatment, any new or worsened clinically significant abnormalities should be recorded as adverse events on the Adverse Event eCRF.

#### **4.5.4      Vital Signs**

Vital signs will include measurements of respiratory rate, pulse rate, and systolic and diastolic blood pressure while the patient is in a seated position, and temperature.

Any abnormality identified at screening or prior to initiation of study treatment should be recorded on the General Medical History and Baseline Conditions eCRF (unless considered related to a protocol-mandated intervention). After initiation of study treatment, any new or worsened clinically significant abnormalities should be recorded as adverse events on the Adverse Event eCRF.

#### **4.5.5      Electrocardiograms**

Single 12-lead ECG recordings will be obtained at specified timepoints (see [Appendix 1](#) and [Appendix 2](#)) and may be obtained at unscheduled timepoints as indicated.

All ECG recordings must be performed on a device that is equipped with reliable, automated algorithms for measuring heart rate and ECG intervals and capable of local printing. Paper copies of ECG tracings will be kept as part of the patient's permanent study file at the site.

Lead placement should be as consistent as possible. ECG recordings should be performed after the patient has been resting in a supine or semi-supine position for at least 10 minutes, and the patient should remain in a supine or semi-supine position during recording. The same positioning should be maintained for each patient throughout the study. ECG recordings should be performed prior to *invasive* procedures scheduled at that same time (e.g., blood draws) and should not be performed within

2.5 hours after any meal. *Vital sign measurements, physical examinations, and diary training may be conducted prior to performing the ECG.* Circumstances that may induce changes in heart rate, including environmental distractions (e.g., television, radio, conversation), should be avoided during the pre-ECG resting period and during ECG recording.

Paper copies of all ECG tracings must be reviewed, annotated to indicate any clinical findings, signed, and dated by a medically qualified member of the site staff. For each timepoint, heart rate, RR interval, PR interval, QRS interval, uncorrected QT interval, and QTcF based on machine readings of ECG tracings should be recorded on the appropriate eCRF. Any morphologic waveform changes or other ECG abnormalities must be documented on the eCRF.

If at a particular postdose timepoint the mean QTcF is >500 ms or >60 ms longer than the baseline value (i.e., last value prior to initiation of study treatment), another ECG must be recorded, ideally within the next 5 minutes, and ECGs should be repeated at least hourly until two successive ECGs show resolution of the findings. A PK sample should be obtained if not already scheduled for that timepoint. The Medical Monitor should be notified, and standard-of-care treatment may be instituted at the discretion of the investigator. A decision on study treatment discontinuation should be made, as described in Section 5.1.2.2. The investigator should also evaluate the patient for potential concurrent risk factors (e.g., electrolyte abnormalities, concomitant medications known to prolong the QT interval, severe bradycardia).

#### **4.5.6            Colonoscopy or Flexible Sigmoidoscopy with Colonic Biopsies**

All patients will undergo either a colonoscopy or flexible sigmoidoscopy with collection of colonic biopsies at baseline/screening, at [REDACTED] or the treatment discontinuation visit. Patients without documentation of a colonoscopy within 2 years prior to screening must have a colonoscopy in lieu of a flexible sigmoidoscopy at screening. Every effort should be made to schedule on-treatment endoscopies on the same day as the protocol-specified study visit.

Bowel preparation prior to the colonoscopy and flexible sigmoidoscopy procedures should be done per local practice. Medications used for bowel preparation should be reported on the Concomitant Medications eCRF. Scheduled stool samples should be taken prior to bowel preparation.

For each patient, a video recording will be performed during the colonoscopy or flexible sigmoidoscopy procedure through use of high-definition video recording per the endoscopy manual.

Video recordings should be taken of the entire endoscopic procedure, starting from insertion into the bowel. Biopsies should be performed upon withdrawal of the

endoscope from the bowel. Technical instructions for video recording and biopsy collection will be provided in the endoscopy and/or laboratory manual.

The clinician who performs the endoscopy may take into account endoscopy findings when completing the Physician's Global Assessment (PGA) subscore of the Mayo Score (see Section [4.5.7.2](#)).

All video recordings will be submitted to a central reading facility to be centrally reviewed for mucosal lesions and endoscopic severity by an independent gastroenterologist experienced in UC who is blinded to the patient's clinical activity, study visit, and treatment allocation. Endoscopic videos will be assessed to determine if patients meet the endoscopic inclusion criterion as well as to objectively document subsequent disease activity. For efficacy assessment of primary, secondary, and exploratory endpoints, Mayo endoscopy subscore will be calculated on the basis of centrally read patient videos. Locally read endoscopic videos will be used to inform investigator-determined clinical or treatment decisions.

#### **4.5.7      Clinical Outcome Assessments**

Clinical outcome assessments of treatment benefit will be primarily collected through the Mayo Score, a composite endpoint incorporating both patient-reported outcome (PRO) and clinician-reported outcome (ClinRO) measures ([Appendix 3](#)).

PRO data will be collected through use of the following instruments: Mayo Score (Stool Frequency and Rectal Bleeding items; [Appendix 3](#)) and Ulcerative Colitis Patient-Reported Outcomes Signs and Symptoms (UC-PRO/SS; [Appendix 4](#)). PRO instruments will capture each patient's direct experience with vixarelimab.

ClinRO data will be collected *using* the Mayo Score Physician's Global Assessment item (PGA; [Appendix 3](#)).

##### **4.5.7.1      Data Collection Methods for Clinical Outcome Assessments**

PRO instruments will be self-administered at home at specified timepoints during the study (see schedule of activities in [Appendix 1](#) and [Appendix 2](#)).

PRO instruments (Rectal Bleeding/Stool Frequency Mayo Score items and UC-PRO/SS), translated into the local language as appropriate, will be completed through use of an electronic device, either the patient's own device or one provided by the Sponsor. The device will be preprogrammed to enable the appropriate instruments to be administered in the correct order at each specified timepoint. The electronic device and instructions for completing the instruments electronically will be provided by the site staff. The data will be transmitted to a centralized database maintained by the electronic device vendor. The data will be available for access by appropriate study personnel.

Patients should be given the following instructions for completing instruments at home:

- Patients should complete the instruments in a quiet area with minimal distractions and disruptions.
- Patients should answer questions to the best of their ability; there are no right or wrong answers.
- Patients should not obtain advice or help from others (e.g., family members or friends) when completing the instruments.

*The ClinRO instrument (the PGA component of the Mayo Score) will be completed at the clinic at specified timepoints during the study (see schedule of activities in [Appendix 1](#) and [Appendix 2](#)). The PGA will be completed prior to the administration of study treatment and entered into the Mayo Clinic Score - Revised eCRF.*

#### **4.5.7.2 Description of Clinical Outcome Assessment Instruments Mayo Score and Modified Mayo Score**

The Mayo Score (including mMS) will be assessed during the study at specified timepoints.

The Mayo Score is a composite of four assessments, each having a scoring range of 0–3: stool frequency, rectal bleeding, endoscopy (score of 1 modified to exclude friability), and PGA. The Mayo Score is the sum of these assessment subscores and has a range of 0–12, with higher scores indicating more severe disease (see [Appendix 3](#)).

The mMS is a composite of three assessments from the Mayo Score, each having a scoring range of 0–3: stool frequency, rectal bleeding, and centrally read endoscopy. The mMS has a range of 0–9, with higher scores indicating more severe disease (see [Appendix 3](#)).

Patients are to report their stool frequency and rectal bleeding, as described below.

#### **Stool Frequency and Rectal Bleeding**

Stool frequency and rectal bleeding are components of the Mayo Score and mMS.

At screening, the patient's normal number of stools, defined as the number of stools passed when a patient is in remission (i.e., not in flare), or prior to the onset of UC if a patient has never been in remission, will be documented.

Patients are to record stool frequency and rectal bleeding daily in their electronic diary (e-diary) during screening and induction, beginning with the first screening visit, and at specified timepoints throughout the study (see [Appendix 1](#) and [Appendix 2](#)). The average stool frequency and rectal bleeding scores from the daily e-diary entries within the [REDACTED] will be used as efficacy baseline and for inclusion. [REDACTED]

[REDACTED]

[REDACTED] If the average stool frequency and rectal bleeding scores are not available from the [REDACTED] the average stool frequency and rectal bleeding scores from the [REDACTED] will be used as the baseline for efficacy assessment and for inclusion.

Because the endoscopy and associated bowel preparation can interfere with the assessment of PROs, e-diary entries on days of bowel preparation, endoscopy, and the day after endoscopy will not be used to calculate any stool frequency or rectal bleeding scores.

### **Physician's Global Assessment**

PGA data will be collected through use of *the Mayo Clinic Score - Revised eCRF*. The PGA is a component of the Mayo Score. The PGA should reflect the clinician's assessment of the patient's current overall status, taking into account stool frequency and rectal bleeding scores, clinician endoscopy findings, patient-reported symptoms, clinician observations, physical examination findings, and other pertinent findings. If possible, the clinician who completes the PGA should not be the same clinician who assesses adverse events. If possible, the same clinician should complete the PGA at each timepoint.

### **Ulcerative Colitis Patient-Reported Outcome Signs and Symptoms**

Patients are to complete the UC-PRO/SS in the e-diary at specified timepoints throughout the study (see [Appendix 1](#) and [Appendix 2](#)).

The UC-PRO/SS is a 9-item daily diary to quantify the effects of treatment on patient-reported signs and symptoms of UC. The UC-PRO/SS assesses the presence of UC symptoms and, in some cases, the severity or frequency of the symptoms (Higgins et al. 2017; Pulley et al. 2021). The UC-PRO/SS includes two domains, Bowel Signs and Symptoms (6 items) and Functional Symptoms (3 items), and yields two separate weekly average scores. Each scale is scored separately; there is no total score. Patients are instructed to complete the diary each evening, reflecting back on their experiences during the past 24 hours. The UC-PRO/SS takes approximately 3 minutes to complete. The UC-PRO/SS will be collected daily during screening and daily over at least a 7-day period before each specified study visit.

Because the endoscopy and associated bowel preparation can interfere with the assessment of PROs, e-diary entries on days of bowel preparation, endoscopy, and the day after endoscopy will not be used to calculate any stool frequency or rectal bleeding scores.

A copy of the UC-PRO/SS instrument is provided in [Appendix 4](#).

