**Table 1 Objectives and Corresponding Endpoints (cont.)**

Exploratory Objectives	Corresponding Endpoints

 
To evaluate the long-term efficacy of vixarelimab
 
	
 
Sustained remission, defined as clinical remission at [REDACTED] Week 12 [REDACTED]
 
Clinical remission at [REDACTED]
 
Clinical response at [REDACTED]
 
Endoscopic improvement at [REDACTED]
 
Endoscopic remission at [REDACTED]
 
Change from baseline in UC bowel movement signs and symptoms at Week 12 and [REDACTED], as assessed by UC-PRO/SS score
 
Improvement in UC bowel movement signs and symptoms at Week 12 [REDACTED], as defined by the proportion of patients with a <math>\geq 6</math>-point decrease in the UC-PRO/SS bowel domain score
 
Change from baseline in UC functional signs and symptoms at Week 12 and [REDACTED], as assessed by UC-PRO/SS score
 
Improvement in UC functional symptoms at Week 12 and [REDACTED], as defined by the proportion of patients with a <math>\geq 2</math>-point decrease in the UC-PRO/SS functional domain score
 

 
To evaluate potential relationships between vixarelimab exposure and the efficacy and safety of vixarelimab
 
	
 
Relationship between PK parameters for vixarelimab and efficacy endpoints
 
Relationship between PK parameters for vixarelimab and safety endpoints
 

 
To evaluate potential relationships between selected covariates and exposure to vixarelimab
 
	
 
Relationship between selected covariates and PK parameters for vixarelimab
 

 
To evaluate potential effects of ADAs
 
	
 
Relationship between ADA status and efficacy, safety, or PK endpoints
 

ADA=anti-drug antibody; PK=pharmacokinetic; UC=ulcerative colitis; UC-PRO/SS=Ulcerative Colitis Patient-Reported Outcomes Signs and Symptoms.

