## Appendix 1: Schedule of Activities for Induction

---

[figure not shown]
- p All women of childbearing potential will have a serum pregnancy test performed at screening. Urine pregnancy tests will be performed at specified subsequent visits during treatment, at the treatment discontinuation visit, and at [REDACTED] after the final dose of study treatment. Urine pregnancy tests will be reviewed prior to each study drug administration for confirmation of a negative result. If a urine pregnancy test is positive, it must be confirmed by a serum pregnancy test.
- q All patients will undergo either a colonoscopy or a flexible sigmoidoscopy at specified timepoints. Patients without documentation of a colonoscopy within 2 years prior to screening must undergo a colonoscopy in lieu of a flexible sigmoidoscopy at screening. The screening endoscopy will be used as efficacy baseline and for inclusion. Video recordings should be taken of the entire endoscopic procedure (colonoscopy or flexible sigmoidoscopy), starting from insertion into the bowel. Biopsies should be performed upon withdrawal of the endoscope from the bowel. Technical instructions for video recording and biopsy collection will be provided in the endoscopy and/or laboratory manual.
- r Tissue collected at screening will be analyzed for CMV, *if required (see Section 4.1.2)*, as determined by histologic examination or immunohistochemistry per local standards, and will undergo histopathologic examination for patients without a prior histopathology report. Tissue collected at screening and subsequent timepoints will also be used for histologic assessments and exploratory biomarker research *at participating sites, excluding China (see Appendix 9)*. *For endoscopy assessments after screening for sites located in China, endoscopy will be performed but no biopsy will be collected.*
- s See [Appendix 3](#). *The Mayo Score will be calculated by the Sponsor.*
- t Clinician-reported outcome instruments will be completed after the physical examination, prior to the administration of study treatment.
- u An electronic diary will be used to collect PRO data, including stool frequency/rectal bleeding and the UC-PRO/SS instrument (see Section 4.5.7.2). Stool frequency and rectal bleeding will be recorded daily; UC-PRO/SS will be collected daily during screening and daily over at least a 7-day period before each specified study visit.

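### The UC-PRO/SS subsection excludes bowel-preparation and endoscopy days from the wrong scores, so as written they stay in the exploratory UC-PRO/SS weekly averages

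*Combined protocol and SAP*

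**What the plan says.** Section 4.5.7.2 describes the UC-PRO/SS as a 9-item evening diary that "yields two separate weekly average scores", one for the bowel domain (6 items) and one for the functional domain (3 items). It is collected daily in screening and then "daily over at least a 7-day period before each specified study visit". The induction schedule footnote in Appendix 1 repeats this: "UC-PRO/SS will be collected daily during screening and daily over at least a 7-day period before each specified study visit". The Appendix 2 footnote uses the same 7-day period for the extension.

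The UC-PRO/SS subsection gives a general reason for dropping some diary days: "Because the endoscopy and associated bowel preparation can interfere with the assessment of PROs". The rule that follows covers preparation days, the endoscopy day and the next day, and says that these entries "will not be used to calculate any stool frequency or rectal bleeding scores". The stool frequency and rectal bleeding subsection ends with the same sentence ("endoscopy, and the day after endoscopy will not be used to calculate any stool frequency or rectal bleeding scores"), and there it fits its subject.

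On timing, Section 4.5.6 says: "Every effort should be made to schedule on-treatment endoscopies on the same day as the protocol-specified study visit".

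Table 1 and Section 6.4.3 list four exploratory UC-PRO/SS endpoints at Week 12: change from baseline in each domain, and improvement "as defined by the proportion of patients with a" decrease of at least 6 points (bowel) or at least 2 points (functional). Section 6.4.3 plans descriptive summaries only.

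**The concern.** The sentence appears to have been carried over without changing the score names. In the UC-PRO/SS subsection it adds nothing to the rule already given for the Mayo items and leaves the UC-PRO/SS without a rule. The protocol therefore treats one diary day as unreliable for stool frequency and rectal bleeding, yet leaves it usable for UC-PRO/SS questions about the number of bowel movements and blood in them. Appendix 4 also asks about liquid stools, leakage and urgency, which bowel preparation would be expected to raise.

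Week 12 requires an endoscopy, because the endoscopic endpoints are assessed there. If preparation days enter the Week 12 average, the score looks worse than the disease is. That understates improvement from baseline and makes the fixed 6-point and 2-point thresholds harder to reach.

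**Working it through.** **Step 1: is there another rule?** The UC-PRO/SS subsection, the schedule footnotes in Appendices 1 and 2, Table 1 and Section 6.4.3 were read together. The footnotes give a collection period only. Table 1 and Section 6.4.3 define endpoints without excluding any day. No readable text takes the affected days out of the UC-PRO/SS averages. The plan states no figure on this point, so there is none to reproduce.

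**Step 2: how many days fall in the window?** The window is the 7 days before the visit. With endoscopy on the visit day, the endoscopy day and the day after lie outside it, which usually leaves one preparation day (k = 1). An earlier endoscopy can bring in up to three (k = 3).

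**Step 3: shift in the weekly mean.** Shift = k × X / 7, where X is the extra domain points on an affected day. The documents give no value for X, so a range is assumed.

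| Domain (threshold) | Assumed X | Shift, k = 1 | Share of threshold |
|---|---|---|---|
| Bowel (6) | 3 to 12 | 0.43 to 1.71 | 7% to 29% |
| Functional (2) | 1 to 4 | 0.14 to 0.57 | 7% to 29% |

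**Step 4: bowel responder rates, Week 12 affected only.** For normally distributed change, responder rate = 1 − Φ((6 + kX/7 − mean improvement) / SD). Assumed mean improvement is 4 on placebo and 7 on active, SD 5.

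- No affected day: 1 − Φ(0.40) = 34.5% and 1 − Φ(−0.20) = 57.9%; difference 23.5 points.
- One day, X = 6: 28.4% and 51.1%; difference 22.8, a loss of 0.7.
- One day, X = 12: 22.9% and 44.3%; difference 21.4, a loss of 2.1.

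**Step 5: what if baseline is affected too?** This was simulated with assumed baseline mean 13 (SD 4), improvement 6 on active and 3.5 on placebo (SD 5), X = 10, and scores held within 0 to 27. That range assumes item 1 is coded 0–7 and the other five bowel items 0–4 (7 + 5 × 4 = 27). Appendix 4 prints no codes for items 1 and 2.

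| Affected days, baseline / Week 12 | Active | Placebo | Responder difference | Difference in mean change |
|---|---|---|---|---|
| 0 / 0 | 48.0% | 29.6% | 18.4 | 2.25 |
| 0 / 1 | 35.6% | 19.9% | 15.7 | 2.21 |
| 0 / 2 | 24.1% | 12.1% | 12.0 | 2.17 |
| 1 / 1 | 47.6% | 29.3% | 18.3 | 2.21 |

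One affected day at Week 12 alone costs 18.4 − 15.7 = 2.7 points of responder difference. With one day in both windows the loss is 0.1. The difference in mean change moves by a few hundredths in every row. Without the bounds, the same inputs give 19.1 falling to 17.2 for one day at Week 12 only.

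**The case against.** The strongest reply is that little depends on this. The endpoints are exploratory and have no planned test. The modified Mayo endpoints rely on stool frequency and rectal bleeding, which the correctly placed sentence protects. A reader might infer that the Week 12 efficacy results as a whole are corrupted; the documents do not support that.

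A second reply is that the intent is plain. The sentence stands in the UC-PRO/SS subsection and gives patient-reported outcomes as its reason. Sections 6 and 6.4 leave detailed methods to a separate Data Analysis Plan, which is not among the documents and may contain the exclusion. So it is not established that these days will be analysed, only that the protocol as written does not exclude them.

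A third reply is that contamination is similar in blinded arms and may be present at baseline, since every patient has a screening endoscopy. Step 5 bears this out: equal contamination removes nearly all of the attenuation. A reader might also infer a general loss of treatment contrast, or that three bad days are typical. The first holds only for responder endpoints under unequal contamination. The second describes endoscopy done before the visit day, which Section 4.5.6 asks sites to avoid.

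What remains is that a stated rule names the wrong scores. The UC-PRO/SS baseline window is not visible in the public text, so cancellation cannot be assumed. Even with cancellation between windows, days that the protocol itself calls unreliable would stay in the averages.

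**Conclusion.** The wording defect is real. As written, preparation, endoscopy and post-endoscopy days are not excluded from the UC-PRO/SS bowel and functional averages. The effect is confined to exploratory, descriptive UC-PRO/SS endpoints at Week 12 and at any later visit with an endoscopy. Primary and secondary endpoints, sample size and error rates are not involved.

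The size is modest. One preparation day shifts the weekly bowel mean by about 0.4 to 1.7 points (X of 3 to 12) and lowers responder rates in both arms. If baseline is not equally affected, the responder difference shrinks by about 2 to 3 points in the scenarios with X of 10 to 12, and by under 1 point in the Step 4 illustration with X = 6. Equal baseline contamination largely removes this, and the between-arm difference in mean change is nearly unchanged. All these sizes rest on assumed values for X, the means, the SDs and the item coding. It should be corrected because the rule is wrong on its face and cheap to repair.

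**What to change.** In the UC-PRO/SS paragraph of Section 4.5.7.2, replace the score names at the end of the exclusion sentence with *UC-PRO/SS bowel and functional domain scores*. State that the rule applies at baseline and at every visit with an endoscopy. Define the weekly average as the mean of the remaining eligible diary days in the window, subject to a stated minimum number, or extend the diary window by the number of excluded days. Carry the same rule into the Data Analysis Plan.

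The cost is one phrase, plus the day-exclusion programming already needed for the Mayo diary items. In a 7-day window, excluding one to three days leaves six to four, so averages rest on slightly fewer entries unless a few more diary days are collected. If the window is to be extended, that must be set before the visits concerned, because only seven days are guaranteed now.
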